13.4 Demographic and Baseline Characteristics

Demographics and baseline characteristics will be summarized separately for Period 1 and for all subjects in the Safety Analysis Set.

Demographic characteristics will include age, sex, race, and ethnicity.

The baseline characteristics will include: weight, height, body mass index (BMI), DXA parameters as reported on CRF (BMD and bone mineral content), Calcium Sensing Receptor (CaSR) genetic

mutation and renal ultrasound status (normal/abnormal), and if abnormal presence of nephrolithiasis and/or nephrocalcinosis. All of the above information will be listed by subject.

Age will be calculated from date of birth to date of first dose in Period 1 (for Cohort 1 subjects) and Period 2 (for Cohort 2 subjects).

13.5 Medical History

Medical history will be mapped to preferred terms (PTs) and system organ classes (SOCs) using the Medical Dictionary for Regulatory Activities (MedDRA®) Dictionary (version 24.0 or later) and summarized by SOC and PT for all subjects in the Safety Analysis Set. Subjects may have more than one medical history term within a SOC and PT. These summaries will present the number and percentage of subjects having each PT. At each summary level subjects are counted once if they had one or more medical history term at that level. The table will be ordered by descending frequency of incidence of PT within each SOC.

All medical history data will be listed.

13.6 Safety Analyses

All safety analyses will be performed on the Safety Analysis Set.

13.6.1 Adverse Events

AE means any untoward medical occurrence associated with the use of an intervention in humans, whether or not considered intervention-related (21 CFR 312.32 (a)).

TEAEs are those which first occur or increase in severity or relationship to study treatment after the first dose of study treatment and not more than 30 days after the last dose of study treatment. All adverse events which change in severity or relationship to study treatment are assigned a new start date and captured as a new record. For subjects in cohort 1, an AE that occurred more than 30 days after the Period 1 last dose of study treatment and before the Period 2 first are not treatment-emergent and are not mapped to a period. Those AEs will be listed separately.

As Period 1 is separate from the other periods, treatment emergence is defined separately for Period 1 and for the other periods; AEs will be mapped to each period for the reporting (see Section 10.8 for more details).

A summary of TEAEs, including the number of events reported, the number and percentage of subjects reporting at least one TEAE regardless of relatedness assessment, the number and percentage of subjects reporting at least one TEAE related to study drug, the number and percentage of subjects discontinuing due to a TEAE, the number and percentage of subjects with at least one serious adverse event, the number and percentage of subjects reporting at least one TEAE of discontinuation of study drug, the number and percentage of subjects reporting at least one TEAE of special interest (symptomatic/asymptomatic hypocalcemia), and the number and percentage of TEAE leading to death (seriousness death) will be presented by period (Period 1, Period 2 + Period 3 and LTE). The same summary will be repeated for AEs.

A breakdown of the number and percentage of subjects with at least one TEAE, categorized by SOC and PT coded according to the MedDRA dictionary, will be presented. Subjects are only counted once within each SOC or PT. The same summary will be repeated for all TEAE related to study drug and for TEAEs leading to discontinuation of study drug.

A summary of events reported, categorized by severity (Mild, Moderate and Severe), will also be provided. Subjects with multiple events within a particular SOC or PT will be counted under the category of their most severe event within that SOC or PT.

Adverse events of special interest will be presented separately by Periods. The number and percentage of subjects with hypocalcemia (symptomatic and/or asymptomatic) as well as number and percentage of subjects for each symptom for symptomatic hypocalcemia will be presented.

All adverse events (including non-treatment-emergent events) recorded on the CRF will be listed.

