# 8.5.3.2 Relationship to Study Intervention

The investigator must assess the relationship of the event to the study drug. The causal relationship of the AE is assessed using a binary system, and AEs are classified as either 'related' or 'unrelated' as defined below.

- **Related**: The available evidence suggests the adverse event is most likely due to the study drug. For example, a temporal relationship exists between the AE onset and administration of the study drug that cannot be readily explained by the study participant's clinical state, concurrent disease or concomitant therapies.
- **Not related**: The available evidence suggests the adverse event is most likely related to factors other than the administration of the study drug. Such other factors may include the underlying disease state, comorbidities, an intercurrent illness, concomitant medication(s) or procedures.
- The investigator may change the causality assessment at any time based on new accumulated information.
- An AE with causal relationship not initially determined will require follow-up to assign causality.

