# 9.6 Safety Analyses

Safety and tolerability parameters will be summarized using descriptive statistics, where appropriate. All safety data will be provided in data listings.

AEs will be coded using the MedDRA dictionary. The incidence of each treatment-emergent AE (TEAE) will be summarized by system organ class, preferred term and treatment assignment. Multiple AEs mapped to the same preferred term will be counted once per participant. Concomitant medications will be coded using the WHO Drug Dictionary with generic term and Anatomical Therapeutic Chemical (ATC) code and summarized by ATC code, WHO Drug generic name, and treatment. Reasons for early termination will be summarized by treatment group assignment. Safety laboratory findings, vital signs, and 12-lead ECGs will be summarized descriptively and listed by treatment assignment and visit. Values and changes from baseline at scheduled time points will be summarized. Laboratory data will be listed and values and changes from baseline at each visit will be summarized. An additional listing of treatment-emergent laboratory abnormalities will be provided.

An AE (classified by preferred term) that occurs during the treatment period will be considered a TEAE if it was not present before the first dose of CLTX-305 (encaleret) or if it was present before the first dose of CLTX-305 (encaleret) but increased in severity during the treatment period. If more than 1 AE is reported before the first dose of CLTX-305 (encaleret) and is coded to the same preferred term, the AE with the greatest severity will be used as the benchmark for comparison with the AEs that were also coded to that preferred term and that occurred during the period. An AE that occurs more than  $30 \pm 7$  days after the last dose of CLTX-305 (encaleret) will not be counted as a TEAE.

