9.0 Study Endpoints, Variables and Covariates

Objectives	Endpoints							
Primary								
 Periods 1, 2, and 3: Evaluate the safety and tolerability of single and multiple doses of CLTX- 305 (encaleret) in subjects with ADH1. 	 Periods 1, 2 and 3: Number of subjects with adverse events (AEs), serious AEs Absolute values and change from baseline in clinical safety (laboratory tests), vital signs, and electrocardiograms (ECGs). AEs and serious AEs (SAEs) – frequency count and percentages of subjects; Clinical safety laboratory tests, vital signs and ECGs – absolute levels and change from baseline. 							
 Period 3: Evaluate the safety, tolerability and efficacy of CLTX-35 (encaleret) in subjects with ADH1 after 24 weeks. 	 Period 3: cCa after treatment with CLTX-305 for 24 weeks - absolute levels and change from baseline. Urinary calcium clearance (fractional excretion) after treatment with CLTX-305 for 24 weeks – absolute levels and change from baseline; Urinary calcium clearance (24-hour total excretion) after treatment with CLTX-305 for 24 weeks - absolute levels and change from baseline. 							
 LTE: Evaluate the longer-term safety and tolerability of CLTX-305 (encaleret) in subjects with ADH1 from Period 3 for approximately 25 months (approximately 2 years). 	 LTE: AEs and SAEs - frequency count and percentages of subjects; Clinical safety laboratory tests and vital signs for approximately 25 months (approximately 2 years) - absolute levels and change from baseline. 							
Secondary								
 Periods 1 and 2: Evaluate the effect of CLTX-305 (encaleret) to increase serum iPTH levels after both single and multiple doses across a dose range in subjects with ADH1. 	 Periods 1, 2, and 3: Absolute values and change from baseline in iPTH blood concentrations profiles (24-hours) over time after single and multiple doses of CLTX-305 (encaleret). 							

Objectives	Endpoints							
Secondary								
 Evaluate the PK of both single and multiple ascending doses of CLTX- 305 in subjects with ADH1 where intensive PK sampling was done. 	• PK parameters: maximum plasma concentration (C_{max}) , time to maximum plasma concentration (t_{max}) , apparent terminal half-life $(t_{\frac{1}{2}})$, area under the concentration-time curve (AUC) from time 0 to the last measurable time point (AUC _{0-t}), AUC from time 0 to 24 hours (AUC _{2-cu}) AUC							

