10.8 Treatment-emergent Adverse Event (TEAE)

For subjects in Cohort 1, AEs will be considered treatment-emergent to Period 1 if they have missing or partial start dates for which it cannot be determined whether the AE started before or after the Period 1 or Period 2 first dose of study medication.

For subjects in Cohort 2, AEs will be considered treatment-emergent to Period 2 if they have missing or partial start dates for which it cannot be determined whether the AE started before or after the Period 2 first dose of study medication.

As there will be no interruption of study drug treatment between Period 2, Period 3 and LTE, those 3 periods will be considered only one period and referred to Period 2 in the below definitions.

Period 1

Treatment-emergent AEs (TEAEs) are defined as any AE(s) or SAE(s), regardless of relationship to study drug, that have an onset or worsening in severity on or after the first dose of study drug until 30 days after Period 1 last dose of treatment date.

Period 2

TEAEs are defined as any AE(s) or SAE(s), regardless of relationship to study drug, that have an onset or worsening in severity on or after the Period 2 first dose of study drug until 30 days after the last dose of treatment in the study.

Each AE is mapped to a Period based on their start date, using the rules defined in Table 2. If the start date is partial, determination of the Period will based on the imputed start date (see Section 10.11 for details). If the date is entirely missing, the AE will be assigned to Period 1 for subjects in Cohort 1 and to Period 2 for subjects in Cohort 2.

Cohort	Analysis Period	Start of the Period	End of the Period
	1*	Data of ICE	If the subject continued in Period 2: last dose in Period 1 + 30 days.
	1.	Date of ICF	If the subject did not continue in Period 2: all AEs are assigned to Period 1.
1	2	Date of Outpatient	If the subject continued in Period 3: last dose in Period 2.
	2	Admission Visit	If the subject did not continue in Period 3: Date of completion/discontinuation of the study
	3	Last dose date in Period 2 + 1 day	If the subject continued in LTE: last dose in Period 3.
			If the subject did not continue in LTE: Date of completion/discontinuation of the study
	LTE	Last dose date in Period 3 + 1 day	Date of completion/discontinuation of the study
	2		If the subject continued in Period 3: last dose in Period 2.
2	2	Date of ICF	If the subject did not continue in Period 3: all AEs are assigned to Period 2.

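### SAP 13.6.1 makes a causality upgrade treatment-emergent and re-dates the event, contrary to SAP 10.8 and Protocol 9.6, so one ongoing AE can be counted twice as a TEAE

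*SAP*

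**What the plan says.** SAP 13.6.1 defines emergence with three limbs: "TEAEs are those which first occur or increase in severity or relationship to study treatment after the first dose of study treatment". It then adds a record rule: "All adverse events which change in severity or relationship to study treatment are assigned a new start date and captured as a new record". For details of period-specific emergence it sends the reader to SAP 10.8.

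SAP 10.8 has no causality limb. A Period 1 TEAE is an AE or SAE, "regardless of relationship to study drug, that have an onset or worsening in severity on or after the first dose of study drug"; the Period 2 wording is parallel. The same section fixes where an event is reported: "Each AE is mapped to a Period based on their start date".

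Protocol 9.6 agrees with 10.8. An event is treatment-emergent if it is new after first dose, or was "present before the first dose of CLTX-305 (encaleret) but increased in severity during the treatment period". SAP 6.1, which lists changes from the protocol, does not mention a causality criterion.

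Protocol 8.5.3.2 uses a two-level causality scale (related or not related) and states: "The investigator may change the causality assessment at any time based on new accumulated information".

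**The concern.** A causality revision changes a judgement about an event; nothing new has happened to the participant. Under 13.6.1 it nevertheless has two effects on the data. A move from not related to related meets the TEAE definition in its own right. Any move, in either direction, also creates a second record with a later start date.

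The TEAE overview in 13.6.1 reports a number of events as well as numbers of subjects, and it does so separately for Period 1, Periods 2 and 3 together, and the LTE. Double-counting and misplacement in time are therefore both possible. Two programmers working from different sections of the same SAP could produce different TEAE tables from the same data.

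**Working it through.** The documents contain no figure to reproduce. The check is to apply each rule to simple hypothetical AE histories and count the result.

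**Rules**
- Rule 1: onset or increased severity only (SAP 10.8, Protocol 9.6).
- Rule 2: the 13.6.1 definition, meaning onset, increased severity or increased relationship.
- Rule 3: every split record with a start date after first dose is counted as an onset.

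**Histories.** First dose is Day 1. The LTE is taken to start on Day 189, the lower bound of the first LTE window in SAP Table 4. Severity is constant except in the last row.

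| History | Rule 1 events | Rule 2 events | Rule 3 events | Effect on subject count (Rule 1 to Rule 2) |
|---|---|---|---|---|
| Onset Day 10, upgraded to related Day 20 | 1 | 2 | 2 | none (1 to 1) |
| Onset Day -5, upgraded to related Day 20 | 0 | 1 | 1 | 0 to 1 |
| Onset Day 10 as related, downgraded Day 20 | 1 | 1 | 2 | none (1 to 1) |
| Onset Day 150 (Period 3), upgraded Day 200 (LTE) | 1 | 2 | 2 | none overall; the LTE column gains the subject |
| Onset Day -5, severity increased Day 20 | 1 | 1 | 1 | none (1 to 1) |

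**What follows**
1. Each upgrade of an ongoing AE adds one TEAE under 13.6.1.
2. A downgrade does not meet the 13.6.1 definition. It adds an event only if the split record, with its new start date, is read as an onset. Because that reading is open under 10.8 too, correcting the definition sentence alone would not be enough.
3. A subject count rises only in two situations: a pre-dose AE is upgraded after dosing without worsening, or the new start date falls in a later reporting period. In both, the subject must also have no other event at that level in that period.
4. Where that does happen, one subject weighs 100/16 = 6.25 percentage points at the planned maximum of 16 treated, 100/8 = 12.5 at the Period 1 maximum of 8, and 100/5 = 20 at the Period 1 minimum of 5. These figures are the weight of one subject. They are not the size of a typical effect.
5. The total effect is (number of upgrades) × 1 event. The documents do not give the number of upgrades.

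**The case against.** The strongest reply is that the primary endpoint is not at risk. SAP 9.0 words it as "Number of subjects with adverse events (AEs), serious AEs", which is not a TEAE count. In the TEAE tables by SOC and preferred term each subject is counted a single time, as Protocol 9.6 also provides. The overview is repeated for all AEs, and every AE is listed. A reader might infer from 13.6.1 that the primary safety endpoint is inflated; the documents do not support that. A subject with a pre-dose AE is already in the all-AE summary, and a post-dose AE upgraded within a period leaves the subject count unchanged. This part of the reply stands, except that re-dating can still add a subject to a later period.

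A reader might also infer that any change in causality makes an event treatment-emergent. The definition requires an increase; only the record rule speaks of a change.

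The pre-dose case is remote. In a drug-naive participant, an event that began before the first dose would have to be attributed to the drug afterwards with no worsening. Protocol 8.1 labels AEs before dosing as baseline, and Protocol 8.5.4 does not treat conditions present at screening as AEs. Carry-over from Period 1 to Period 2 in Cohort 1 is conceivable but uncommon.

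Finally, 13.6.1 refers to 10.8, the summaries are descriptive (Protocol 9.1), and the error over-counts events and does not hide any. These points limit the consequence. They do not remove the conflict, because the relationship wording and the record rule remain in the section that specifies the tables.

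**Conclusion.** The conflict is real and 13.6.1 is the outlier: SAP 10.8 and Protocol 9.6 agree with each other, and the departure is not declared in SAP 6.1. Followed as written, 13.6.1 gives a wrong TEAE event count (one extra per causality upgrade) and can place an ongoing AE in a later reporting period, for example the LTE. Subject-level TEAE percentages change only in the two situations described, and the subject-level primary AE endpoint is largely protected.

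This is a minor point. It assumes that programming takes 13.6.1 literally and that some causality assessments are revised while an event is ongoing. How often that happens is not given and is likely small, so no overall percentage effect can be stated.

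**What to change.** 1. In SAP 13.6.1, delete the reference to relationship to study treatment from both the TEAE definition and the record rule, and name 10.8 as the only TEAE definition.
2. State that when only causality changes, the original record and start date are kept and the final causality is reported. The SAP currently has no rule for which assessment counts once a record has been split.
3. Keep the new-record rule for severity changes. Collapsing each episode to its worst severity would go too far: Protocol 8.5.4 requires severity changes to be documented so that time at each level can be assessed. It could also move a worsening seen in the LTE back to an onset in Period 3.

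The cost is an edit to two sentences, one added sentence, and a small programming step to rejoin any records already split for causality alone. No new data are needed.

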#### Rationale for the Long-term Extension (LTE)

Participants who have completed Period 3 and continue to meet study eligibility criteria may continue in a Long-term Extension (LTE) for continuous safety evaluation of CLTX-305 (encaleret). The primary objective of LTE is to assess the longer-term safety and tolerability of CLTX-305 (encaleret) in ADH1 participants. The secondary objective will be to obtain long-term efficacy (durability) data of CLTX-305 (encaleret) treatment with respect to mineral homeostasis and related measures.

The LTE is designed to obtain additional safety data for CLTX-305 (encaleret). Participants who elect to continue in LTE will receive CLTX-305 (encaleret) for an additional period of time, up to 25 months (approximately 2 years) or until they transition to the CLTX-305-302/CALIBRATE Phase 3 LTE, whichever occurs first.

At any point during the LTE, and before transition to the CLTX-305-302/CALIBRATE Phase 3 LTE, participants can choose to stop participation and be placed back on the conventional therapy. Follow-up assessments should be completed per Schedule of Assessments (see Section 1.3 Table D).

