Period 1 is an inpatient stay that consists of 5 dosing days during which subjects will undergo a once daily (QD) dose escalation for 3 days followed by 2 days of BID dosing at an individualized test dose of CLTX-305 (encaleret). Note: Tau will be 9 hours for the am dose and 15 hours for the pm dose.

Period 2 is an inpatient stay that consists of 5 dosing days during which subjects will receive BID doses of CLTX-305 based on individual responses from Period 1 (for subjects who complete Period 1) or review of aggregate data from Period 1 (for subjects in Cohort 2 entering Period 2 without prior exposure to CLTX-305 [encaleret]). The initial dose, dose-level 1 (DL1) will be administered for 2 days (48 hours) with cCa monitoring. Participants will undergo encaleret dose up- or down-titration depending on cCa levels, with a potential increase in dose if cCa remains below the lower limit of normal and potential decrease in dose if cCa is greater than or equal to the upper limit of normal. A final test day (Day 5) will include frequent blood and urine sampling to collect 24-hour PK/PD profiles.

Dosing guidance for Period 1 and Period 2 are shown in Figure 3 and Figure 4.

Figure 3: Dosing Guidance for Period 1

Figure 4: Dosing Guidance for Period 2

BID= Two doses/day

Period 3 is an outpatient dosing period that consists of administration of CLTX-305 (encaleret) for up to 24 weeks. Subjects completing Period 2 will continue to self-administer CLTX-305 (encaleret) at an initial BID dose based on their tolerance and response to BID dosing during Period 2. Initial titration will be based on each subject's need for symptom control and ongoing monitoring of efficacy endpoints (primarily cCa and urine calcium excretion) with a goal to optimize cCa in the normal range

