13.3 Treatments

13.3.1 Extent of Study Drug Exposure

Exposure data will be summarized for Period 3 and LTE only using the Safety Analysis Set. The average daily dose for each period will be summarized for each period. The average daily dose will be derived as the sum of the dose levels times the number of days on each dose, divided by the number of days in the period considered. Additionally, the number of missed doses by period will be summarized.

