13.6.2 Deaths and Serious Adverse Events

Serious TEAEs and serious TEAEs related to study treatment will be summarized by SOC and PT for each Period and overall.

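### Adverse events are tabulated by period only as counts and crude percentages, with no participant-time, although at-risk time runs from about 35 days to about 25 months or longer

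*SAP*

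**What the plan says.** The treatment-emergent overview in SAP 13.6.1 "will be presented by period (Period 1, Period 2 + Period 3 and LTE". Its measures are the number of events and, for example, "the number and percentage of subjects reporting at least one TEAE regardless of relatedness assessment". In the system organ class and preferred term tables, "Subjects are only counted once within each SOC or PT". Serious events "will be summarized by SOC and PT for each Period and overall" (SAP 13.6.2), and adverse events of special interest are shown separately by period. SAP 11.1 sets the denominator as subjects dosed in the period concerned.

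The periods differ widely in length. "Period 1 is an inpatient stay that consists of 5 dosing days" (SAP 8.0), and an event counts as emergent in Period 1 if it starts or worsens "on or after the first dose of study drug until 30 days after Period 1 last dose of treatment date" (SAP 10.8). Period 2 has another 5 dosing days and Period 3 up to 24 weeks. The LTE lasts up to 25 months or "until they transition to the CLTX-305-302/CALIBRATE Phase 3 LTE, whichever occurs first" (Protocol 2.1), and entry is elective.

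On exposure, SAP 13.3.1 says "Exposure data will be summarized for Period 3 and LTE only using the Safety Analysis Set". It asks for average daily dose and missed doses. Neither Protocol 9.6 nor the visible SAP asks for duration of exposure, total participant-years or an exposure-adjusted rate. SAP 10.13 and 10.15 are not in the available text, so this statement does not cover them.

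**The concern.** The percentage of subjects with at least one event grows with the length of the window even when the underlying rate is flat. Longer-term safety and tolerability is the primary LTE objective, and the study has no control arm. A reader asking whether events change with time on drug has only the period summaries to set against each other.

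The protocol itself raises that question. Protocol 2.3.1 expects calcium and phosphate fluctuations to be more frequent early, during dose finding, and Protocol 8.5.7 places the risk of symptomatic hypocalcemia before an effective dose is reached. A true fall in rate after titration could therefore appear as a higher percentage in the LTE. The LTE percentage is also hard to interpret alone, because it depends on how long each participant was followed.

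**Working it through.** The documents give no event rate and no calculation behind these tables, so there is no stated figure to reproduce. The rates below are assumptions. They span 0.1 to 5 events per participant-year.

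**Windows**
- Period 1: 5 + 30 = 35 days (SAP 8.0 and 10.8).
- Periods 2+3: 5 + 24 × 7 = 173 days. The Week 24 target in SAP Table 3 is Study Day 174. The table uses 173; in the 0.25 and 1 per year rows, 174 gives the same whole percentages.
- LTE, full length: 25 × 30.4375 = 761 days. SAP 8.0 equates 25 months with about 104 weeks, but 761 / 7 = 108.7 weeks; 24 months is 104.4 weeks.
- Ratio: 35 : 173 : 761 = 1 : 4.9 : 21.7.

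**Formula.** With a constant rate r per year, P(at least one event) = 1 − exp(−r × days / 365.25). At r = 0.25 the exponents are 0.25 × 35 / 365.25 = 0.024, 0.25 × 173 / 365.25 = 0.118 and 0.25 × 761 / 365.25 = 0.521.

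| Assumed rate per year | Period 1 | Periods 2+3 | LTE, 25 months |
|---|---|---|---|
| 0.1 | 1.0% | 4.6% | 18.8% |
| 0.25 | 2.4% | 11.2% | 40.6% |
| 0.5 | 4.7% | 21.1% | 64.7% |
| 1 | 9.1% | 37.7% | 87.5% |
| 2 | 17.4% | 61.2% | 98.4% |
| 5 | 38.1% | 90.6% | 100.0% |

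**A falling rate.** Reading across two rows: 1 per year in Periods 2+3 gives 37.7%, and half that rate over a full LTE gives 64.7%.

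**LTE length.** At 0.25 per year the LTE percentage is 11.8% at 6 months, 22.1% at 12 and 39.3% at 24. Follow-up must exceed 173 / 30.4375 = 5.7 months before it passes Periods 2+3. Protocol 8.2.5 describes about 48 further months in CALIBRATE. If all of that were counted (25 + 48 = 73 months), the figure would be 78.1%.

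**Period 2 as its own column.** If the serious event and special interest tables show it alone, the window for continuing subjects is about 5 days, since SAP Table 2 ends it at the last Period 2 dose. Expected percentages are then 0.3% at 0.25 per year and 1.4% at 1 per year.

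**Chance variation.** Binomial simulation (200,000 runs, constant rate, full LTE) used 5/10/10 and 8/16/16 subjects in the three columns. The probability that percentages never fall across the columns was 0.89 to 0.998. The probability of a strict rise at both steps was 0.19 to 0.98; it was lowest for rare events and was reduced by saturation at 5 per year.

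**Period 1 precision.** Five subjects give 5 × 35 / 365.25 = 0.48 participant-years, and eight give 0.77. One event is then 1 / 0.48 = 2.1 or 1 / 0.77 = 1.3 per participant-year. Of the window, 30 / 35 = 86% is off drug.

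**The case against.** A reader might infer that the SAP compares the periods, or that its tables are bound to show rising incidence. The documents support neither. The SAP presents periods and plans no test between them. Under SAP 12.0, Periods 1 to 3 go into the CSR and the LTE into an addendum, so the three columns need not share a page. SAP 9.0 defines the LTE adverse event endpoint as counts and percentages of subjects, and the tables deliver that. The rise is an expectation at assumed rates; at this sample size rare events can tie or reverse.

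Nor can one infer that reported LTE follow-up stops at transition. Protocol 10.8.3 and SAP 10.14 bring these participants' CALIBRATE LTE data into this study's CSR. That makes the LTE window less predictable and possibly longer, so the imbalance remains.

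Participant-time is not wholly absent either. The average daily dose in SAP 13.3.1 divides by days in the period, event counts are tabulated, and everything is listed. With up to 16 treated participants a determined reader could rebuild the denominator for Period 3 and the LTE, although no planned table prints it.

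The objection also limits the remedy. A Period 1 rate would mix 5 days on drug with 30 days after conventional treatment resumes, in Cohort 1 only. SAP 13.6.1 opens a fresh record when severity or relationship changes, so a raw event rate would count some episodes twice. Protocol 8.2.3 allows a drug gap between Week 24 and LTE entry, whereas SAP 10.8 assumes no interruption. Rates also do not correct for denser calcium sampling in the inpatient periods. These points shape the fix but do not remove the need for it.

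**Conclusion.** The point stands as a limit on what the safety tables can show. Window lengths differ by about 22-fold between Period 1 and a full LTE, and by 761 / 173 = 4.4-fold between Periods 2+3 and a full LTE. No planned summary gives the time denominator. Crude percentages over such windows cannot separate a change in event frequency from a change in follow-up.

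The calculation assumes a constant rate, the same for all subjects, and complete follow-up of each window. The direction of the expected effect holds at every rate tried, provided mean LTE follow-up is well above 5.7 months; its size depends on the rate. Nothing here contradicts the protocol, and the planned percentages are correct as descriptions.

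**What to change.** Keep the crude percentages and add the following.

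- **SAP 13.3.1:** report duration of exposure and total participant-years for every period, and print participant-years in the adverse event column headers.
- **SAP 13.6.1 and 13.6.2, for Periods 2+3 and the LTE, including the addendum:** give exposure-adjusted rates for TEAEs, serious events and events of special interest. Report both subjects with a first event per participant-year (time counted to that event) and events per participant-year.
- **Counting rules:** count once any event re-recorded only because severity or relationship changed. Base time at risk on the SAP 10.8 period mapping. Leave out of both numerator and denominator any off-drug gap between Week 24 and LTE entry beyond the 30-day treatment-emergent window. Count CALIBRATE follow-up in the denominator wherever its events are counted.
- **Period 1:** print participant-days on drug and in the 30-day follow-up separately, and do not use a Period 1 rate to judge trend.

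The cost is small: dose and event dates are already collected, and days in the period are already derived for Period 3 and the LTE. The downside is a few extra columns, a short set of time-at-risk rules, and rates that will be imprecise at this sample size.
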